- Flavivirus serology testing is to determine if a participant is flavivirus seronegative or flavivirus seropositive at baseline. This is not an enrollment criterion. However, this flavivirus serology testing needs to be performed on a blood sample collected prior to administration of the first vaccination to confirm that the study distribution among subgroups is respected.

Follicle-stimulating hormone level may be measured to confirm menopausal status at the discretion of the investigator.

- ⁶ Blood samples must be collected before injection on vaccination days (Days 1 and 29).
- At Visit 5 (Day 57), an additional blood sample (60 mL) will be collected for exploratory research (Table 9 and Section 11.1.10) from participants enrolled at 1 US site. This site will be different from those sites selected for cellular immunity.
- Pregnancy testing at the Eligibility Visit (Day 0) and before each IP injection (or at any time at the discretion of the investigator) will be a point-of-care urine test.
- Participants will be administered the IP (mRNA-1893 or placebo) according to the randomization. Participant will remain at the study site for safety monitoring for at least 30 minutes after IP injection.
- Trained study personnel will call all participants to collect information relating to any MAAEs, SAEs, AESIs, AEs leading to study discontinuation, concomitant medications associated with those events, and any nonstudy vaccinations.
- Blood samples collected from all participants at Visit 6 (Day 85) and Visit 10 (Day 196) will be used for detection of asymptomatic flavivirus infections. In case of signs or symptoms suggesting a flavivirus infection (mostly dengue and Zika in the areas where the study will be performed), an additional blood sample will be collected to confirm the diagnosis via specific serology and RT-PCR, and clinical information will be carefully collected to evaluate the severity of the clinical case. Those symptoms are not specific; however, an association of acute fever onset with maculopapular rash, arthralgia, and conjunctivitis during the seasonal circulation of mosquitos must trigger samplings. Also, special attention will be paid to the reporting of neurological signs or symptoms evoking Guillain-Barré syndrome.

12 At Visit 10 (Day 196), all participants will have the opportunity to provide their consent to participate in the Extension Period (Table 2).

ModernaTX, Inc.

09 Dec 2021

Protocol: mRNA-1893-P201, Amendment 3 mRNA-1893

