5.1. Inclusion Criteria

Participants are eligible to be included in the study only if all the following criteria apply:

1. Male or female participant aged 18 through 65 years at the time of consent.

2. Understands and agrees to comply with the study procedures and provides written informed consent.

- 3. According to investigator assessment, is in good general health and can comply with study procedures.
- 4. Female participants of nonchildbearing potential may be enrolled in the study. Nonchildbearing potential is defined as surgically sterile (history of bilateral tubal ligation, bilateral oophorectomy, hysterectomy) or postmenopausal (defined as amenorrhea for ≥ 12 consecutive months prior to the eligibility evaluation without an alternative medical cause). The follicle-stimulating hormone (FSH) level may be measured at the discretion of the investigator to confirm postmenopausal status.
- 5. Female participants of childbearing potential may be enrolled in the study if the participant:
 1) has a negative pregnancy test at the Eligibility Visit and on the day of the first IP injection, 2) has practiced adequate contraception or has abstained from all activities that could result in pregnancy for at least 28 days prior to the first IP injection, 3) has agreed to continue adequate contraception through 3 months following the last IP injection, and 4) is not currently breastfeeding.

Adequate female contraception is defined as consistent and correct use of a Food and Drug Administration (FDA)-approved contraceptive method in accordance with the product label (Table 16). Examples are as follows:

- Barrier method (such as condoms, diaphragm, or cervical cap) used in conjunction with spermicide.
- Intrauterine device.
- Prescription hormonal contraceptive taken or administered via oral (pill), transdermal (patch), subdermal, or IM route.
- Sterilization of a female participant's monogamous male partner prior to entry into the study.

Note: periodic abstinence (eg, calendar, ovulation, symptothermal, post-ovulation methods) and withdrawal are not acceptable methods of contraception.

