8.2. Clinical Laboratory Assessments

8.2.1. Baseline and Safety Laboratory Assessments

There are no screening criteria based on the flavivirus serostatus, meaning all participants are enrolled regardless of serostatus. However, this baseline flavivirus status will be confirmed by serology testings (dengue IgG and IgM, West Nile IgG and IgM) performed on a blood sample collected prior to administration of the first vaccination in order to eventually ensure that an approximate equal distribution of participants among subgroups is respected for the statistical analysis.

A point-of-care urine pregnancy test will be performed at the Eligibility Visit and before each IP injection (or at any time at the discretion of the investigator) for all female participants of childbearing potential.

The FSH level may be measured at the discretion of the investigator to confirm menopausal status.

There are no screening safety laboratory tests at the time of the eligibility evaluation of the participant. However, additional tests may be performed for safety reasons at any time during the study if determined necessary by the investigator or required by local regulations. Specifically, if the participant presents with signs or symptoms evoking a flavivirus infection, standard-of-care tests and treatment will apply, and results will be reported in the source documents and in the AE section of the eCRF.

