8.5.2. Safety Telephone Calls

A safety telephone call is a telephone call made to the participant by trained site personnel. This call will follow a script, which will facilitate the collection of relevant safety information. The participant will be interviewed according to the script, and information will be collected about the occurrence of any MAAEs, SAEs, AESIs, or AEs leading to study withdrawal, concomitant medications associated with those events, and any nonstudy vaccinations.

The timing of the safety telephone calls is provided in Table 1.

All safety information described by the participant must be documented in source documents and not documented on the script used for the safety telephone contact.

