8.5.3. Physical Examination

A full physical examination will include, at a minimum, assessments of the cardiovascular, respiratory, gastrointestinal, and neurological systems according to standard medical practice. Weight and height will be recorded and BMI will be calculated (body weight [kg] ÷ height [m]²) during the eligibility evaluation.

A symptom-directed physical examination will be performed at the discretion of the investigator each time the participant is in the clinic when a full physical examination is not otherwise specified. Symptom-directed physical examinations will include, at a minimum, inspection of the general status of the participant, according to standard medical practice. Additional elements of the physical examination should be added on the basis of symptoms described during the interview of the participant. Prior to IP injection and at follow-up visits, female participants should also be queried for new onset of menarche.

Investigators should pay special attention to clinical signs related to previous serious illnesses. Treatment of any abnormality observed during physical examination should be performed according to local medical practice outside the study or by referral to an appropriate healthcare provider at the discretion of the investigator. Any clinically significant finding identified during a study visit should be reported as an MAAE.

Significant new findings that begin or worsen after informed consent must be recorded on the AE page of the eCRF.

Protocol: mRNA-1893-P201, Amendment 3

8.5.4. **Vital Sign Measurements**

Vital sign measurements will include body temperature (preferred route is oral), systolic and diastolic blood pressure, heart rate, and respiratory rate. The participant will be seated for at least 5 minutes before all measurements are taken. Vital signs will be collected prior to study procedures and at least 30 minutes after IP injection, prior to discharge of the participant from the study site.

Febrile participants at Day 1 and Day 29 Visits (fever is defined as a body temperature \geq 38.0°C/100.4°F) may be rescheduled within the relevant window periods.

When procedures overlap and are scheduled to occur at the same time point, the order of procedures should be vital sign measurements and then the blood collection.

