8.6.6. Pregnancy

Details of all pregnancies occurring in female participants after the administration of IP must be reported to the Sponsor or designee within 72 hours of learning of the pregnancy following the procedures outlined in Appendix 2. Abnormal pregnancy outcomes (eg, spontaneous abortion, fetal death, stillbirth, congenital anomalies, ectopic pregnancy) are considered SAEs.

Further information on the collection of pregnancy information is given in Appendix 2.

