11.3.3. Collection of Pregnancy Information

Pregnancies occurring in participants after enrollment must be reported to Sponsor or designee within 24 hours of the site learning of its occurrence.

Female Participants Who Become Pregnant

- The investigator will collect pregnancy information on any female participant who becomes pregnant while participating in this study. Information will be recorded on the appropriate form and submitted to the Sponsor within 72 hours of learning of a participant's pregnancy.
- The participant will be followed to determine the outcome of the pregnancy (including spontaneous miscarriage, elective termination, normal birth, or congenital abnormality). The investigator will collect follow-up information on the participant and the child, even if the participant is discontinued from the study, and the information will be forwarded to the Sponsor. Generally, follow-up will not be required for longer than 6 to 8 weeks beyond the estimated delivery date. Any termination of pregnancy will be reported, regardless of fetal status (presence or absence of anomalies) or indication for the procedure.
- While pregnancy itself is not considered to be an AE or SAE, any pregnancy complication or elective termination of a pregnancy will be reported as an AE or SAE. Spontaneous miscarriages, congenital anomaly, and/or birth defect abortion should be reported as SAEs.

• Any post-study, pregnancy-related SAE considered reasonably related to the mRNA-1893 by the investigator will be reported to the Sponsor as described in Section 7.1. While the investigator is not obligated to actively seek this information in former study participants, he or she may learn of an SAE through spontaneous reporting.

Any female participant who becomes pregnant while participating in the study will discontinue mRNA-1893 or be withdrawn from the study.

11.4. APPENDIX 4: CDC Working Case Definitions of Myocarditis, Pericarditis, and Myopericarditis Occurring After Receipt of COVID-19 mRNA Vaccines

Table 17: Case Definitions of Probable and Confirmed Myocarditis, Pericarditis, and Myopericarditis

Condition	Definition		
Acute	Probable Case	Confirmed Case	

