6.3.2. Pregnancy Tests

A point-of-care urine pregnancy test will be performed at the Screening Visit (Day 0) and before each vaccine dose. At any time, a pregnancy test either via blood or point-of-care urine can be performed, at the discretion of the investigator. A by-subject listing will be provided for pregnancy tests.

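### Protocol Section 8.5.3 asks adult women about onset of menarche, and no pregnancy test or named pregnancy question is scheduled after Day 29, so uncomplicated pregnancies may be under-ascertained

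*Protocol*

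**What the plan says.** Protocol Section 8.5.3 (Physical Examination) gives this instruction: "Prior to IP injection and at follow-up visits, female participants should also be queried for new onset of menarche". The first inclusion criterion in Section 5.1 reads "Male or female participant aged 18 through 65 years at the time of consent".

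On testing, Section 8.2.1 says "A point-of-care urine pregnancy test will be performed at the Eligibility Visit and before each IP injection". The same sentence also lets the investigator test at any other time. SAP Section 6.3.2 repeats that allowance: "At any time, a pregnancy test either via blood or point-of-care urine can be performed, at the discretion of the investigator". Table 1 places the scheduled tests on Days 0, 1 and 29. Table 2, for the Extension Period, has no pregnancy row, and neither does SAP Appendix F.

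On questioning, Section 8.5.2 describes the safety calls: "information will be collected about the occurrence of any MAAEs, SAEs, AESIs, or AEs leading to study withdrawal", together with related medications and nonstudy vaccinations. The site interview in Section 8.6.2 covers unsolicited AEs, SAEs and medications. Neither section names pregnancy.

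On reporting, Section 8.6.6 requires that "Details of all pregnancies occurring in female participants after the administration of IP must be reported to the Sponsor or designee", and Sections 11.2.7 and 11.3.3 add follow-up to outcome. Section 11.3.3 also states: "While pregnancy itself is not considered to be an AE or SAE, any pregnancy complication or elective termination" is reportable as an AE or SAE. Section 8.6.6 classes abnormal outcomes as SAEs.

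**The concern.** The protocol wants every pregnancy reported and followed, but the one reproductive question it prescribes cannot detect one. In adults, new onset of menarche is not a plausible finding. The other scheduled questions are about adverse events, and an uncomplicated pregnancy is not an adverse event under the protocol's own definition. A visit to a practitioner for a normal pregnancy is not an MAAE either, because Section 11.2.4 defines an MAAE as a kind of AE.

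The two kinds of pregnancy therefore have different routes into the database. One that ends in loss or anomaly can be picked up by a scheduled question. One that proceeds normally needs the participant to volunteer it or the investigator to test on his or her own initiative.

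This matters more here than in many vaccine trials. Section 2.2 names microcephaly and spontaneous abortion among the harms of Zika infection, so pregnancy outcomes after this vaccine will be read closely. A count of losses means little without a complete count of pregnancies beneath it.

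**Working it through.** No figure in the plan bears on this, so the check is a count of contacts and a comparison of detection routes.

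**Contacts after the last scheduled test (Tables 1 and 2)**

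- Clinic visits: Days 36, 57, 85, 196, 364, 532 and 700, which is 7.
- Safety calls: Days 112, 140 and 168, which is 3.
- Total: 7 + 3 = 10. With a scheduled pregnancy test or a named pregnancy question: 0.
- For a participant who declines the Extension Period: 4 visits + 3 calls = 7, again with 0.

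**Time without a scheduled test**

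- To Day 196: 196 − 29 = 167 days.
- To Day 700: 700 − 29 = 671 days.
- The contraception commitment runs 3 months past the last injection, to about Day 29 + 91 = Day 120. The contacts on Days 36, 57, 85 and 112 fall inside it. None has a scheduled check.

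**Routes to detection after Day 29**

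| Route | Uncomplicated pregnancy | Complication, loss or anomaly |
|---|---|---|
| Menarche query (8.5.3) | No | No |
| Scheduled AE, SAE and MAAE questions (8.5.2, 8.6.2) | No, not an AE | Yes |
| Spontaneous disclosure | Yes | Yes |
| Test at the investigator's choice | Yes | Yes |

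Medication records are not a dependable substitute. Section 6.5.2 ends general recording 28 days after the last injection.

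**What this does to an observed share**

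Let L be the true share of pregnancies with an abnormal outcome, p the chance that such a pregnancy is found, and q the chance that an uncomplicated one is found. Then

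observed share = pL / (pL + q(1 − L)).

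This exceeds L exactly when p is greater than q. The table shows one extra route for abnormal outcomes, which is a reason to expect p above q. The documents give no value for p, q or L, and no number of women of childbearing potential or conception rate. Direction can be argued; size cannot be computed.

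**The case against.** The best defence is that the plan is not confined to bad outcomes. It requires every pregnancy the site learns of to be reported and followed, and normal birth is a listed outcome (Section 11.3.3). Pregnancy report forms go to sites (Section 11.2.7). Pregnancy bars further injection (Section 7.1) and is a recorded reason for withdrawal (Section 7.3). Testing is allowed at any time, and participants have up to 10 later contacts at which to mention a pregnancy. The call script and eCRF are not among the documents and may already hold a pregnancy item. All arms are questioned alike under an observer-blind design, and the SAP plans no pregnancy-outcome proportion, only a listing of pregnancy tests.

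Most of this stands as a limit on the claim. It does not remove it. The reporting duties begin once the site knows of a pregnancy; they do not create the knowledge. Discretionary testing needs a prompt, and no scheduled question supplies one. The unseen script and eCRF mean the documents support only that no pregnancy question is named, not that none is asked.

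Two stronger readings are tempting. A reader might infer that pregnancies will be found mainly when they go wrong. The documents do not show that: disclosure and discretionary testing can find normal pregnancies, possibly most of them, and an early or unrecognised loss can escape general AE questions too. A reader might also infer that pregnancies will be learned of too late to report. That fails, because the reporting clock starts when the site learns of the pregnancy, and Section 11.2.7 continues follow-up beyond the end of the study's safety follow-up.

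**Conclusion.** The point holds in limited form. The menarche query is uninformative in this population, and it is the only reproductive question the protocol names. After Day 29, 0 of 10 contacts has a scheduled pregnancy test or a named pregnancy question. Finding an uncomplicated pregnancy rests on disclosure or discretion, while abnormal outcomes also have a scheduled route. Ascertainment may therefore be skewed toward abnormal outcomes, and the reporting duty may be met incompletely.

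The size of any skew is unknown. A numerical range would rest wholly on assumed numbers of women, conception rates, loss rates and detection rates, so none is given. No bias between arms is shown, and the immunogenicity and main safety analyses are not affected. What could mislead is a share of abnormal outcomes read on its own or against an outside background rate. The conclusion assumes that neither the call script nor the eCRF already carries a pregnancy question. If one does, Section 8.5.3 still needs correcting and the protocol should name the item.

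**What to change.** First check whether the call script or eCRF already holds a pregnancy item. Then:

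- In Section 8.5.3, replace the menarche query with a question on any pregnancy since the last contact, put to women of childbearing potential at existing visits and safety calls. When first asked of someone already enrolled, it should reach back to the first injection.
- Name the item in Section 8.5.2 and give it a row in Tables 1 and 2 (and SAP Appendices E and F).
- In the SAP, add a listing of pregnancies and their outcomes by arm, covering all pregnancies found. Section 6.3.2 now lists only pregnancy tests.
- In the same edit, reconcile the reporting deadlines. Sections 8.6.6 and 11.2.7 give 72 hours; Section 11.3.3 gives both 24 and 72 hours.

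No new visit or scheduled test is needed. The cost is a little site time at each contact, changes to the script and eCRF where the item is absent, and a formal amendment with IRB/IEC approval under Section 11.1.7 in a study that is already enrolling.

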8.6.1. Time Period and Frequency for Collecting AE and SAE Information

Medical occurrences that begin before the first vaccination with mRNA-1893 but after obtaining informed consent will be recorded in the Medical History/Current Medical Conditions section of the eCRF, not in the AE section; however, if the condition worsens at any time during the study, it will be recorded and reported as an AE.

The time periods for collection, recording, and reporting of solicited ARs, unsolicited AEs, and SAEs are found in Appendix 2.

Adverse events may be collected as follows:

• Observing the participant.

Receiving an unsolicited complaint from the participant.

• Questioning the participant in an unbiased and nonleading manner.

Solicited ARs will be collected from the day of injection through 6 days after each IP injection (Days 1 through 7 and Days 29 through 35). Other (unsolicited) AEs will be collected from the day of injection through 28 days after each IP injection (Days 1 through 29 and Days 29 through 57).

Serious AEs will be collected from the first IP injection until the last follow-up visit after the last IP injection at the time points specified in the SOAs (Table 1 and Table 2).

All SAEs will be recorded and reported to the Sponsor or designee immediately, and under no circumstance should this exceed 24 hours, as indicated in Section 11.2.11. The investigator will submit any updated SAE data to the Sponsor within 24 hours of it being available.

An abnormal value or result from a clinical or laboratory evaluation (eg, a radiograph, an ultrasound, or an electrocardiogram) can also indicate an AE if it is determined by the investigator to be clinically significant (eg, leads to dose modification or study drug discontinuation or meets any serious criteria). If this is the case, it must be recorded in the source document and as an AE on the appropriate AE page of the eCRF. The evaluation that produced the value or result should be repeated until that value or result returns to normal or is stabilized and the participant's safety is not at risk.

Investigators are not obligated to actively seek AEs or SAEs after conclusion of the study participation. However, if the investigator learns of any SAE, including a death, at any time after a participant has been discharged from the study, and he/she considers the event to be reasonably related to the IP or study participation, the investigator must promptly notify the Sponsor.

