4. STUDY DESIGN

4.1. General Design

This is a Phase 2, randomized, observer-blind, placebo-controlled, dose confirmation study.

All participants will be evaluated for their eligibility (Section 4.1.1) for enrollment in the Vaccination Period and will be followed for approximately 6 months (Day 196) after their last IP injection (Section 4.1.2). Table 1 displays the Schedule of Assessments (SOA) for all participants through Day 196. All participants in all treatment arms will have the opportunity to continue to be followed as part of an approximately 24-month Extension Period (through Day 700) after their last IP injection (Section 4.1.3). Table 2 displays the SOA for participants who continue into the Extension Period through Day 700. The study design is illustrated in Figure 1.

A total of approximately 800 participants will be randomly assigned to receive either µg or µg mRNA-1893 administered as a 2-dose regimen with at least a 28-day interval between vaccinations (Treatment Arm A or Treatment Arm B), or µg mRNA-1893 administered as a 1-dose regimen (Treatment Arm C), or placebo control administered as a 2-dose regimen with at least a 28-day interval between doses (Treatment Arm D) according to a 1:1:1:1 randomization ratio (ie, 200 participants per treatment arm with approximately 100 participants per baseline flavivirus serostatus in each treatment arm). Randomization was stratified by participants' baseline flavivirus serostatus assessed by a rapid dengue point-of-care test on site in the original protocol (dated 21 Feb 2021). Under the current protocol amendment, randomization will be stratified only by participants' region (continental US and Puerto Rico). All treatment arms will be enrolled in parallel. In order to maintain the blinding and to have the same study evaluation time point with both mRNA-1893 dose regimens relative to the last IP injection, participants randomly assigned to Treatment Arm C will be administered placebo at Day 1 and mRNA-1893 at Day 29 (Table 6).

Table 6: Treatment Arms

	Study Day	
	Day 1	Day 29
Treatment Arm A	mRNA-1893 μg First vaccination	mRNA-1893 μg Second vaccination
Treatment Arm B	mRNA-1893 μg First vaccination	mRNA-1893 μg Second vaccination
Treatment Arm C	Placebo	mRNA-1893 μg First vaccination
Treatment Arm D	Placebo	Placebo

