6.3.1. Adverse Events

An AE is defined as any untoward medical occurrence in a subject or clinical investigation subject who is administered a pharmaceutical product at any dose that does not necessarily have to have a causal relationship with the treatment.

A treatment-emergent AE (TEAE) is defined as any event occurring during the study not before exposure to study vaccine or any event already present that worsens after exposure to study vaccine. Adverse events will also be evaluated by the investigator for the coexistence of MAAE which is defined as an AE that leads to an unscheduled visit to a healthcare practitioner.

Unsolicited AEs will be coded by PT and SOC using MedDRA summarized by baseline flavivirus serostatus, vaccination group, and stage (up to 28 days after each vaccination, up to 28 days after any vaccination and overall stage; see Section 6.1 for definitions of vaccination group and stage).

All summary tables (except for the overall summary of AEs) for unsolicited AEs will be presented by SOC and PT for TEAEs with counts of subjects included. SOC will be displayed in internationally agreed order. PT will be displayed in descending order of frequency of total mRNA-1893 and then alphabetically within SOC. When summarizing the number and percentage of subjects with an event, subjects with multiple occurrences of the same AE or a continuing AE will be counted once. Subjects will be presented according to the highest severity (the strongest relationship) in the summaries by severity (of related AEs), if subjects reported multiple events under the same SOC and/or PT.

Percentages will be based upon the number of subjects in the Safety Set within each vaccination group.

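### Protocol 8.6.1 starts adverse-event recording at the first mRNA-1893 vaccination instead of the first IP injection, which conflicts with its own collection windows and cannot be applied by blinded staff

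*Protocol*

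**What the plan says.** Protocol 8.6.1 begins: "Medical occurrences that begin before the first vaccination with mRNA-1893 but after obtaining informed consent will be recorded in the Medical History/Current Medical Conditions". Entries made there are kept apart from the adverse events, with one exception for worsening. In the protocol's words, they go "not in the AE section; however, if the condition worsens at any time during the study, it will be recorded and reported as an AE". On this wording, the cut-off between Medical History and the AE section is the first dose of active vaccine.

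Under Protocol 4.1, "participants randomly assigned to Treatment Arm C will be administered placebo at Day 1 and mRNA-1893 at Day 29", and Table 6 labels Arm C's Day 29 injection as its first vaccination. Arm D receives "placebo control administered as a 2-dose regimen with at least a 28-day interval between doses (Treatment Arm D"), so it never receives mRNA-1893.

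Further down, 8.6.1 uses a different starting point: "Other (unsolicited) AEs will be collected from the day of injection through 28 days after each IP injection", given as Days 1 to 29 and Days 29 to 57. Solicited reactions follow each IP injection in the same way, and SAEs are collected from the first IP injection. IP includes placebo. Footnote 9 to Table 1 in Section 1.3 reads: "Participants will be administered the IP (mRNA-1893 or placebo) according to the randomization".

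The SAP (6.3.1) defines a treatment-emergent AE as "any event occurring during the study not before exposure to study vaccine", or an existing event that worsens after that exposure. Protocol 11.2.1 ties treatment emergence to exposure to the IP.

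**The concern.** In a trial where every participant receives mRNA-1893 on Day 1, the opening sentence would do no harm. Here two of the four arms receive saline on Day 1. For them the sentence puts the start of AE recording later than the first injection, or never.

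The sentence decides which eCRF page an event goes on, and unsolicited AEs are a primary safety endpoint assessed against placebo. If any events were filed as Medical History on the strength of this sentence, placebo rates and Arm C's rate after its saline injection could be understated. Vaccine-minus-placebo differences would then look larger than they are.

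The rule also needs information that its users lack. Under Protocol 6.3.2 the investigator and study staff are blinded to the product given.

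**Working it through.** No planned figure rests on this sentence, so the check is mainly a comparison of texts, followed by a count of how far the literal wording reaches.

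**Applying the opening sentence alone to a new event on Day 10**

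| Arm | Day 1 | Day 29 | Where the sentence files it |
|---|---|---|---|
| A or B | mRNA-1893 | mRNA-1893 | AE section |
| C | placebo | mRNA-1893 | Medical History, unless it worsens |
| D | placebo | placebo | Unclear: Medical History if a dose never given counts as always still ahead; otherwise the rule does not apply |

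**Other text on when an event counts as an AE**

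- Protocol 8.6.1, later paragraphs: from the day of each IP injection, or from the first IP injection for SAEs.
- Protocol 11.2.1 (Appendix 2): conditions first found once IP has been given are AEs, and treatment emergence is judged against the IP.
- Protocol 8.6.2: the investigator documents AEs in every treatment group.
- Protocol 4.5: saline recipients have the same safety follow-up as vaccine recipients.
- Protocol 8.5.3: significant new findings that start after consent go on the AE page, which is a third starting point.
- SAP 6.1: the overall safety stage starts at the Day 1 injection in all arms.
- SAP 9.4: an AE with no start date is pre-treatment if it ended before the first injection, and otherwise treatment-emergent.

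For Arm C the Day 10 event is Medical History under the first paragraph of 8.6.1 and an AE under the later ones. No text says which governs.

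**Reach of the literal sentence**

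Inputs: 200 participants per arm (Protocol 4.1, Table 7), and two 28-day windows, each the injection day plus 27 more (Protocol 8.5, SAP 6.1).

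- All planned person-days: 4 × 200 × 2 × 28 = 44,800.
- Arm D, if the sentence applies to it: 200 × 2 × 28 = 11,200.
- Arm C, first window only: 200 × 28 = 5,600.
- Total reached: 11,200 + 5,600 = 16,800, and 16,800 / 44,800 = 37.5%.
- Participants reached after injection 1: (200 + 200) / 800 = 50%.
- Arm C alone, if the sentence is held not to apply to Arm D: 5,600 / 44,800 = 12.5%.
- With the cut-off at the first IP injection: 0 of 44,800.

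**The case against.** A reader might infer that, as written, the protocol leaves every placebo event and every Arm C event before Day 29 out of the AE data, and so biases every comparison with placebo. The documents do not support that, for four reasons.

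1. The inference reads one sentence in isolation. The rest of 8.6.1 and Sections 4.5, 8.6.2 and 11.2.1 call for AE collection in all arms from the IP injections. Solicited reactions have their own route through the eDiary and the Reactogenicity page (8.5.1, 11.2.3), and worsening is excepted in the sentence itself.
2. For Arm D the sentence has no reference point. Reading it as inapplicable is at least as natural as reading it to cover everything.
3. Blinding cuts both ways. A rule that sites cannot apply by arm cannot, by itself, selectively remove placebo events. Confusion and site queries are the likelier result.
4. The SAP does not clearly repeat the error. It treats vaccination group and treatment arm as interchangeable (Section 1) and lists Placebo among the vaccination groups (6.1). In defining the FAS it refers to study vaccination (5.4) where the protocol refers to IP (9.3.4). Its safety stage and AE-date rules run from the first injection.

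All four stand. They remove the claims of lost data and of demonstrated bias, and they reduce the SAP wording to a matter of tidying. They do not rescue the opening sentence. It is an operative filing instruction, it is unambiguous for Arm C, and it conflicts with the text around it.

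**Conclusion.** The concern holds as an internal contradiction in a recording rule. The opening sentence of 8.6.1 uses a starting point that does not fit a trial with a placebo arm and a placebo-first arm. It conflicts with the IP-based rules in the same section and in 11.2.1, and blinded staff cannot follow it.

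Its literal reach is 37.5% of planned person-days over the two windows if Arm D is covered, and 12.5% if only Arm C is. Both figures assume 200 per arm with complete follow-up in both windows. Neither estimates missing events. A differential effect on AE rates would also require someone filing events to know or guess the product given and to follow this sentence over the rest of the protocol. The documents give no sign of that, so understated placebo or Arm C rates are a possibility only.

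The correction is still worth making, because the sentence governs how a primary safety endpoint is recorded.

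**What to change.** In Protocol 8.6.1, reconcile the opening sentence with the rest of the section by moving the cut-off from the first mRNA-1893 vaccination to *before the first IP injection (mRNA-1893 or placebo)*. The cost is one phrase, by amendment or by a clarification to sites. No new data are needed.

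Optionally, in SAP 6.3.1, replace *study vaccine* with *IP* in the treatment-emergent definition so that it matches Protocol 11.2.1. This is tidying only.

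If reassurance is wanted about records already entered, a blinded listing of Medical History entries with onset after the first injection would show whether any event was misfiled. It uses data already held.
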